### 3.5.2 Secondary Efficacy Assessments

#### 3.5.2.1 GEBT $T_{1/2}$ and Timepoints

The value, change from baseline, and percent change from baseline in gastric emptying BT  $T_{1/2}$  as measured by GEBT at Day 14 ( $\pm 2$  days) will be summarized by treatment group. The value and time-matched (to baseline visit) change from baseline and percent change from baseline of the GEBT results for each post-meal timepoint will also be summarized by treatment group.

#### 3.5.2.2 ANMS GCSI-DD

The ANMS GCSI-DD is scheduled to be completed daily starting at least 14 days prior to randomization through Day 14. The ANMS GCSI-DD will be summarized using two different scoring methods: the protocol specified method and the scoring method as indicated in the User Manual for the ANMS GCSI-DD (section 4.2, September 27, 2018 version). For both methods, baseline for analysis will be defined as the average score for the 3 days preceding randomization.

Both total ANMS GCSI-DD and the subscale scores (and change and percent change from baseline values) will be summarized by treatment group for each scheduled assessment.

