### **4.3 Randomization Criteria**

In addition to the general criteria listed in [Sections 4.1](#) and [4.2](#), in order to be randomized into the study, subjects must also meet the following criteria at the time of randomization:

- Continues to satisfy all inclusion/exclusion criteria.
- Has been off all motility agents and antiemetics for at least 14 days and is willing to remain off such medications (except for protocol-specified antiemetic rescue medication) during the course of the study.

- Demonstrates a confirmed diagnosis of idiopathic or diabetic gastroparesis as defined by the following:
  - Current upper GI symptoms (eg, nausea/vomiting, postprandial fullness, early satiety, bloating, and/or epigastric/ abdominal pain).
  - Documented DGE within the 10 days prior to first dose of study drug based on GEBT using  $^{13}\text{C}$ -spirulina platensis demonstrating  $T_{1/2} > 80$  minutes. Subjects with a  $T_{1/2} > 200$  minutes may be considered for the study with sponsor approval.

[REDACTED]

[REDACTED]

[REDACTED]

[REDACTED]

[REDACTED]

[REDACTED]

[REDACTED]

[REDACTED]

- Has continued required results of the initial safety laboratory test performed at Screening.

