##### 3.5.2.2.1 Protocol Specified Scoring Method

The ANMS GCSI-DD covers 5 core relevant symptoms of gastroparesis: nausea, early satiety, postprandial fullness, upper abdominal pain and vomiting. Bloating is included as an exploratory symptom. Symptoms are rated on a severity numeric response scale from 0 (none) to 4 (very severe). Vomiting is captured on a frequency response scale and scored as follows: 0 for no episodes, 1 for one episode, 2 for 2 episodes, 3 for 3 episodes, and 4 for 4 or more episodes. Subjects will be asked to recall symptoms over the previous 24 hours and complete the ANMS GCSI-DD patient-reported symptom questionnaire for at least 14 days prior to randomization, on the day of randomization, and daily from Days 1 to 14 ( $\pm 2$  days).

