##### 3.5.2.2.2 ANMS Manual Scoring Method

The severity scores of four gastroparesis-related symptoms (nausea, early satiety, postprandial fullness, upper abdominal pain) range from 0-none to 4-very severe. The vomiting score assesses the number of vomiting episodes during the day, capped at a maximum of 4; thus, the scores for vomiting range from 0 (no episodes of vomiting) to 4 (four or more episodes of vomiting). Vomiting frequency is scored as 0 episodes, 1 episode, 2 episodes, 3 episodes, or 4 or more episodes (capped as 4).

The ANMS GCSI-DD total gastroparesis symptom daily score is generated by summing the scores on each of the five symptom items (nausea, early satiety, postprandial fullness, upper abdominal pain, and number of vomiting episodes) and then dividing by 5, that is the number of items within the gastroparesis related symptom score. Thus, the maximum total symptom score could be (5 symptoms \* maximum score 4 divided by 5); hence, the maximum score is 20/5=4. The ANMS GCSI-DD gastroparesis symptom daily score can range from 0 to 4. High scores on the ANMS GCSI-DD reflect greater symptom severity.

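### The GCSI-DD summaries compare single diary days with a 3-day baseline; a pre-specified 7-day mean on each side would remove avoidable noise at almost no cost

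*SAP*

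**What the plan says.** SAP 2.3.2 lists change from baseline in GCSI-DD total and subscale scores among the secondary efficacy variables. It ties the neighbouring breath-test half-time variable to Day 14 but gives no day or window for the GCSI-DD variables. SAP 2.1 and Protocol 2.2 place symptoms under the exploratory objectives.

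SAP 3.5.2.2 says the diary "is scheduled to be completed daily starting at least 14 days prior to randomization through Day 14". SAP 3.5.2.2.1 confirms the daily schedule: "on the day of randomization, and daily from Days 1 to 14", with a window of ±2 days on the last day. For both scoring methods, "baseline for analysis will be defined as the average score for the 3 days preceding randomization".

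After baseline, total and subscale scores, with change and percent change, "will be summarized by treatment group for each scheduled assessment". The unit being scored is one day: SAP 3.5.2.2.2 states that "The ANMS GCSI-DD total gastroparesis symptom daily score is generated by summing the scores on each of the five symptom items", and its description of the manual's method stops at that daily score, which runs from 0 to 4.

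The readable text names no weekly mean, no target day and no minimum number of completed diary days for these variables. Protocol 7.3 is redacted, Protocol 7.2 is redacted in part, and the user manual that the SAP cites is not among the documents.

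**The concern.** A daily symptom score carries day-to-day fluctuation, and a daily diary allows it to be averaged out. As the SAP reads, the averaging is short on the baseline side (3 of at least 14 days) and absent on the treatment side (one day at a time). Every tabulated change therefore carries the full error of one post-baseline day.

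The groups are small: about 15 per treatment. If placebo is not pooled for efficacy (SAP 3.2), each cohort has only 5 placebo subjects. Protocol 1.3 says that the results will support dose selection for later studies, so imprecise symptom summaries have a practical cost even without a test. With no designated window, any weekly average made later would not be pre-specified.

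A smaller issue sits in the same sentence. Percent change is required for scores that can be 0, and it is undefined when the baseline is 0.

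**Working it through.** **Plan's own figure.** There is none to reproduce for the GCSI-DD. SAP 2.2.7 gives a head count without a formal calculation. It is consistent with the cohort design: 3 cohorts × (15 + 5) = 60, with 15 on placebo in total.

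**Inputs from the documents.** Baseline days b = 3; post-baseline days p = 1 in each summary; diary daily for at least 14 days before randomisation and through Day 14.

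**Assumptions (not in the documents).** Daily error variance is set to 1 unit. Day-to-day autocorrelation is AR(1) with φ = 0, 0.3, 0.5 or 0.7. Subject-level variance in true change, τ, is 0, 0.25, 0.5 or 1 in the same units; averaging days cannot remove it. The single day is placed at Day 14 for illustration only.

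**Formula.** Var(change) = V(b) + V(p) − 2C + τ. Here V(k) = (1/k)[1 + 2 Σ (1 − j/k) φ^j], summed over j = 1 to k − 1, and C is the covariance between the two means. C is negligible here for φ up to 0.5 and small at 0.7.

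**Step 1: independent days, τ = 0.**
- Current rule (3/1): 1/3 + 1 = 1.333. The single day supplies 1 of 1.333, or three quarters.
- 7-day means on both sides (7/7): 1/7 + 1/7 = 0.286. SD ratio √(0.286/1.333) = 0.463, a 54% cut.
- Longer baseline only (7/1): 1/7 + 1 = 1.143. SD ratio √(1.143/1.333) = 0.926, a 7% cut.
- Longer endpoint only (3/7): 1/3 + 1/7 = 0.476. SD ratio √(0.476/1.333) = 0.598, a 40% cut.

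**Step 2: autocorrelated days, τ = 0.** Example at φ = 0.5: V(3) = (1/3)[1 + 2(0.333 + 0.083)] = 0.611, so the current rule gives 1.611.

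| φ | 3/1 variance | 7/7 variance | SD ratio |
|---|---|---|---|
| 0 | 1.33 | 0.29 | 0.46 |
| 0.3 | 1.49 | 0.48 | 0.57 |
| 0.5 | 1.61 | 0.69 | 0.66 |
| 0.7 | 1.74 | 1.01 | 0.76 |

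**Step 3: add τ to both variances.** Reduction in SD of change, 7/7 against 3/1:

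| τ | φ = 0 | 0.3 | 0.5 | 0.7 |
|---|---|---|---|---|
| 0 | 54% | 43% | 34% | 24% |
| 0.25 | 42% | 35% | 29% | 20% |
| 0.5 | 35% | 30% | 25% | 18% |
| 1 | 26% | 23% | 19% | 14% |

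Over the same grid, lengthening only the baseline from 3 to 7 days cuts the SD by 4% to 9%.

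**Step 4: one illustration in score points.** Assume a daily SD of 1 point and a correlation of 0.6 between days within a subject, so the daily error variance is 0.4. Take τ = 0.2 points² (0.5 times that) and φ = 0.3.
- SD now: √(0.4 × 1.487 + 0.2) = 0.89.
- SD with 7/7: √(0.4 × 0.481 + 0.2) = 0.63.
- 95% half-width, 15 v 15: 1.96 × SD × √(2/15), which falls from 0.64 to 0.45 points.
- 95% half-width, 15 v 5: 1.96 × SD × √(1/15 + 1/5), which falls from 0.90 to 0.63 points.

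**Percent change.** SAP 3.5.2.2.1 scores vomiting 0 for no episodes. If vomiting is reported as its own score, a subject with none over the baseline days has a zero denominator. The SAP gives no rule for this.

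**The case against.** The strongest reply is that nothing is being tested. The SAP specifies descriptive summaries only, symptoms are an exploratory objective, and a last-3-days baseline is defensible in itself. All of that stands and lowers the priority.

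Several stronger readings are tempting, and the documents do not support them:
- A reader might infer that the key contrast is Day 14 against baseline. The SAP never says so; it gives no GCSI-DD day special status.
- A reader might infer that post-baseline data are discarded. They are not: every day is summarised. What is missing is a summary window.
- A reader might take 54% as the gain. That is the best case, with independent days and no variation in true change. With no variance figures in the documents, only a range can be given.
- A reader might infer that a long list of daily tables invites picking the best day. All days are shown, table layouts are in a separate document, and one table with a row per day would fit the wording.
- A reader might infer that subjects with a zero baseline are lost. They drop only from percent change; absolute change keeps them. A zero total is unlikely, because Protocol 4.3 requires current symptoms.
- A reader might conclude that no weekly rule exists anywhere. The redacted protocol text and the unavailable manual prevent that claim. It can only be said that the readable text states none. If one is intended, the SAP should state it.

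**Conclusion.** The point holds as a precision improvement to a descriptive analysis. As the SAP reads, each GCSI-DD change compares one diary day with a 3-day mean, and the single post-baseline day is the main source of avoidable noise.

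Seven-day means on both sides would reduce the SD of change by about 24-54% with no between-subject variation in true change. With that variance at 0.25 to 1 times the daily error variance, the reduction is about 14-42%. The direction is the same in every case tried; the size rests on the assumed φ and τ. These figures describe raw change scores, not a covariate-adjusted analysis. The 3-day baseline alone is a minor matter. The point is of lower priority, because symptoms are an exploratory objective even though SAP 2.3.2 lists the scores as secondary variables.

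**What to change.** In SAP 3.5.2.2, pre-specify as the main GCSI-DD summary, for both scoring methods:
- **Baseline:** the mean of the last 7 diary days before randomisation. These fall inside the washout required by Protocol 4.3 ("Has been off all motility agents and antiemetics for at least 14 days").
- **Endpoint:** the mean of the last 7 diary days on treatment, counted back from the subject's actual last treatment day. Fixed Days 8-14 would not fit the ±2-day window: a subject finishing on Day 12 would contribute only five treatment days, and one finishing on Day 16 would lose the last two.
- **Completeness:** at least 4 of the 7 days completed on each side.

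Keep the daily summaries as supportive. For any subscale or item score that is 0 at baseline, report absolute change only; those subjects stay in the absolute-change summary. A baseline covariate is optional, since the plan is descriptive.

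The cost is SAP wording and some programming; the planned diary already collects the data. The downside is that the mean blurs any change within the last treatment week, which the daily summaries would still show.

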### 3.5.3 Exploratory Efficacy Assessments

#### 3.5.3.1 PAGI-SYM

The PAGI-SYM questionnaire on gastroparesis symptoms is completed on Days 1 and 14 and includes 6 subscales: heartburn/regurgitation, fullness/early satiety, nausea/vomiting, bloating, upper abdominal pain, and lower abdominal pain. The total and subscale scores will be derived based on the PAGI-SYM Information Booklet (section 5, 2nd Edition, 2015). Both total and subscale PAGI-SYM scores, along with change from baseline and percent change from baseline, will be summarized by treatment group.

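### Subject-level percent change does not suit infrequent GCSI-DD components such as vomiting: it is undefined at a zero baseline, and its median can show improvement with no drug effect

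*SAP*

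**What the plan says.** SAP 3.5.2.2 (ANMS GCSI-DD) states: "Both total ANMS GCSI-DD and the subscale scores (and change and percent change from baseline values) will be summarized by treatment group". The same sentence says that these scores "will be summarized by treatment group for each scheduled assessment". The diary is completed daily, so this reads as a separate summary for each day. For the denominator, "baseline for analysis will be defined as the average score for the 3 days preceding randomization".

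The scales start at zero. In SAP 3.5.2.2.1 vomiting is scored "0 for no episodes, 1 for one episode, 2 for 2 episodes, 3 for 3 episodes, and 4 for 4 or more episodes", and the other symptoms are rated from 0 (none) to 4. For the total, SAP 3.5.2.2.2 says "The ANMS GCSI-DD gastroparesis symptom daily score can range from 0 to 4".

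For the exploratory questionnaire, SAP 3.5.3.1 says: "Both total and subscale PAGI-SYM scores, along with change from baseline and percent change from baseline, will be summarized by treatment group".

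Four other places bear on the point:

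- SAP 2.3.2 names the change from baseline in GCSI-DD total and subscale scores as secondary variables. It does not name percent change.
- SAP 3.1.4 reports n, mean, median, SD, minimum and maximum. Its only rule for zeros concerns PK geometric means.
- Protocol 4.3 requires current upper GI symptoms, and any one of several is enough. A subject who does not vomit is therefore eligible.
- SAP 3.2 plans about 15 subjects per group and does not pool placebo across cohorts for efficacy, which leaves 5 per cohort.

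**The concern.** A percent change needs a positive baseline. A subject with no vomiting on the three baseline days has a baseline of 0, so the quantity does not exist for that subject. The visible text has no rule for this case, and the default result is a missing value.

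The missingness is selective. A subject at 0 can stay at 0 or get worse, but cannot improve. The percent-change column therefore keeps only subjects with room to improve and loses every new onset of the symptom.

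Among those kept, the denominator is coarse. With a baseline of 1/3 (one episode in three days), a daily score of 0 gives -100% and a score of 1 gives 100 × (1 - 1/3)/(1/3) = +200%. With a baseline of 2/3, the same scores give -100% and +50%. Any day without vomiting gives -100%, whatever the baseline was.

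At stake is a secondary symptom table in which an arm of about 15 with no drug effect can show a large median improvement.

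**Working it through.** The plan states no figure for percent change and no sample-size calculation, so there is nothing to reproduce. The check asks what the percent-change column would show with no drug effect.

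**Inputs from the SAP.** Vomiting scored 0 to 4 and capped at 4; baseline = mean of 3 days; follow-up = one day.

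**Assumed inputs.** The documents give no symptom distribution. Daily vomiting is taken as Poisson with a subject-specific rate drawn from a gamma distribution with mean μ = 0.25 to 1 per day and shape k = 0.3 to 2. The rate is the same before and after treatment.

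**Step 1: share with no percent change.** P(baseline = 0) = (1 + 3μ/k)^(-k).

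- Highest, μ = 0.25, k = 0.3: 3.5^(-0.3) = 69%. Kept of 15: 15 × 0.31 = 4.7.
- Middle, μ = 0.5, k = 1: 1/2.5 = 40%. Kept of 15: 9.0.
- Lowest, μ = 1, k = 2: 2.5^(-2) = 16%. Kept of 15: 12.6.
- At μ = 2 the share is still 4^(-2) = 6% (k = 2) to 21^(-0.3) = 40% (k = 0.3).

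**Step 2: median percent change in subjects with a positive baseline.** Simulation, 400,000 subjects per setting, shape k = 1:

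| Mean episodes/day | Baseline zero | Median, one day vs 3-day mean | Median, 3-day mean vs 3-day mean |
|---|---|---|---|
| 0.25 | 1/1.75 = 57% | -100% | -50% |
| 0.5 | 1/2.5 = 40% | -100% | about -20% |
| 0.75 | 1/3.25 = 31% | -50% | 0% |
| 1 | 1/4 = 25% | -25% | 0% |
| 2 | 1/7 = 14% | 0% | 0% |

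Over shapes 0.3 to 2 and means 0.25 to 1, the one-day median lies between -25% and -100%, and the 3-day median between 0% and -50%. The mean percent change lies between about -30% and +15%. Absolute change in all subjects averages 0.00.

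**Step 3: the selection.** At μ = 0.5, k = 1, the mean absolute change is -0.14 in kept subjects and +0.20 in dropped subjects. Weighted, 0.60 × (-0.14) + 0.40 × 0.20 = -0.084 + 0.080, which is 0 within rounding. The improvement seen in the kept subjects is offset by the worsening in those left out. Across the settings, 6% to 31% of dropped subjects vomited on the follow-up day.

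**Step 4: the second cause.** Give every subject the same rate μ. The one-day score is then 0 with probability e^(-μ), and each such score is -100%. The median is therefore -100% whenever e^(-μ) exceeds 0.5, that is for μ below ln 2 = 0.69. At 0.75 per day only e^(-2.25) = 11% have a zero baseline, yet the exact median is -40%. So setting one day against a 3-day mean drives the result jointly with the zero baselines.

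**Step 5: other scores (assumed latent-normal severity items).**

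- Severity items averaging 0.5: median 0% to -40%.
- Severity items averaging 1: median 0% to -14%.
- Severity items averaging about 1.5 or more: median 0%, zero baselines at most 9%.
- Total score: median 0% in every scenario, zero baselines at most about 5%.

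**The case against.** The strongest reply is that the plan already contains the right analysis. The sentence that plans percent change also plans values and absolute change, and absolute change is the named secondary variable. Subjects with a zero baseline stay in those summaries, and their loss from the percent column would show in its n. The study is a descriptive Phase 2A trial with no formal sample size and no stated hypothesis test on symptoms. All of this stands and limits the harm to one set of columns.

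It is also fair to say that the size rests on an assumed vomiting rate. The visible SAP does not list the GCSI-DD subscales and the matching protocol text is redacted, so separate tabulation of vomiting is not confirmed. The mean is reported beside the median and often points the other way: at shape 1 it is about -4% at 0.5 per day and about +9% at 1 per day. That tempers a claim of uniform false improvement. However, a mean near zero beside a median of -100% is a table that readers cannot use.

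A reader might infer a false advantage for drug over placebo. The documents do not support that: with no drug effect the shift is expected in every arm. What remains is instability. With unpooled placebo, 5 × 0.60 = 3.0 of 5 subjects would be left in the column at 0.5 per day with shape 1. A median on so few is erratic, though that is true of any skewed measure at this size.

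**Conclusion.** The point holds for infrequent components, with vomiting as the clear case if it is tabulated alone. At an assumed 0.25 to 1 episode per day and no drug effect, 16% to 69% of subjects have no percent change. The median in the rest is -25% to -100% for a single day, or 0% to -50% for a 3-day follow-up mean, while absolute change averages 0. At 2 per day the median is 0%, although subjects still drop out.

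Three stronger readings go too far:

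- A reader might apply the 25% to 100% range to the symptom scores in general. The total score and items averaging about 1.5 or more show a median of 0%.
- A reader might say that the plan excludes symptom-free subjects. No such rule is written. Exclusion is what the division produces by default, it affects only the percent column, and a zero total is unlikely given the symptom requirement at entry.
- A reader might extend the figures to PAGI-SYM. The SAP gives no response scale for it, combines nausea with vomiting in one subscale, and uses single assessments on Days 1 and 14 with no 3-day mean. The point carries over only if the scoring allows a zero baseline, and no size can be given.

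The change is worth making because a better summary costs almost nothing. It does not affect the primary endpoint or the named secondary variable.

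**What to change.** In SAP 3.5.2.2:

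1. Delete subject-level percent change for GCSI-DD component and subscale scores. Let absolute change in all subjects lead.
2. If a relative figure is wanted, report percent change of the group mean, 100 × (mean post / mean baseline - 1), with all subjects in both means. With no drug effect the two means have the same expectation, so it centres near 0%, and nobody is dropped unless the whole group has a zero baseline.
3. Compare like with like: set 3-day follow-up means against the 3-day baseline. This alone is not enough, since the median is still about -50% at 0.25 per day.
4. Subject-level percent change may stay for the GCSI-DD total if wanted.

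In SAP 3.5.3.1, do the same for PAGI-SYM subscales if their scoring allows a zero baseline.

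The cost is SAP wording and fewer columns in the symptom tables. The downside is that no subject-level percent change is available for components.

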##### 3.5.2.2.1 Protocol Specified Scoring Method

The ANMS GCSI-DD covers 5 core relevant symptoms of gastroparesis: nausea, early satiety, postprandial fullness, upper abdominal pain and vomiting. Bloating is included as an exploratory symptom. Symptoms are rated on a severity numeric response scale from 0 (none) to 4 (very severe). Vomiting is captured on a frequency response scale and scored as follows: 0 for no episodes, 1 for one episode, 2 for 2 episodes, 3 for 3 episodes, and 4 for 4 or more episodes. Subjects will be asked to recall symptoms over the previous 24 hours and complete the ANMS GCSI-DD patient-reported symptom questionnaire for at least 14 days prior to randomization, on the day of randomization, and daily from Days 1 to 14 ( $\pm 2$  days).

##### 3.5.2.2.2 ANMS Manual Scoring Method

The severity scores of four gastroparesis-related symptoms (nausea, early satiety, postprandial fullness, upper abdominal pain) range from 0-none to 4-very severe. The vomiting score assesses the number of vomiting episodes during the day, capped at a maximum of 4; thus, the scores for vomiting range from 0 (no episodes of vomiting) to 4 (four or more episodes of vomiting). Vomiting frequency is scored as 0 episodes, 1 episode, 2 episodes, 3 episodes, or 4 or more episodes (capped as 4).

The ANMS GCSI-DD total gastroparesis symptom daily score is generated by summing the scores on each of the five symptom items (nausea, early satiety, postprandial fullness, upper abdominal pain, and number of vomiting episodes) and then dividing by 5, that is the number of items within the gastroparesis related symptom score. Thus, the maximum total symptom score could be (5 symptoms \* maximum score 4 divided by 5); hence, the maximum score is 20/5=4. The ANMS GCSI-DD gastroparesis symptom daily score can range from 0 to 4. High scores on the ANMS GCSI-DD reflect greater symptom severity.

